Control participants will be given similar instructions to those who have participated in the standard VR intervention, except they will be exposed to a “sham” intervention that is part of usual hospital care. They will be offered the chance to participate in the study, and if they consent, they will follow the same *Pre-Intervention Procedures* outlined for VR Intervention participants (a physician will collect heart rate and pain data via chart review). Then, the patient will be shown how to use the in-room Health and Wellness relaxation television channel – called the Health and Wellness Channel (<http://www.healinghealth.com/>). The patient will be encouraged to view the channel for approximately 30 minute intervals during the remainder of their hospital stay. After discharge, the physician will collect heart rate and pain data via chart review.

Study Measures

Pain Ratings

As part of usual care, clinical staff regularly obtain assessments of pain intensity from patients using a Numerical Rating Scale (NRS), usually reported on a 0-10 scale, where 0 is no pain, and 10 is the worst pain imaginable. Previous healthcare studies²¹⁻²⁴ have established that NRS is an acceptable method for unidimensional assessment of pain intensity. In this study, patients will not be asked about pain as part of the study. Instead, pain scores reported to the care provider and entered into the EHR will be used.

VR/TV Usage Monitoring

There is no standardized method for assessing viewing time for VR or other audiovisual experiences, without some form of supervision (e.g., automatic, electronic logging on the viewing device; monitoring by study staff; etc.). Currently, we lack the ability to track both TV and VR viewing times through some automated process, so we will provide patients with activity logs, which they will use to record the start time and duration of any viewing experiences (on TV or VR). We realize this method will introduce reporting error, but this error should be equally distributed across both study groups.

HCAHPS

CSMC collects patient satisfaction data using the HCAHPS Picker survey, administered by a third party. In accordance with regulations guiding this survey of patient care experiences, we will not directly influence responses in any way. Instead, we will sample 100% of all study participants, expecting a

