response rate of approximately 25%. We will use these data to estimate changes in satisfaction associated with exposure to the intervention condition, versus the control condition. The HCAHPS survey has demonstrated face validity in previous studies.²⁸

Salivary cortisol assay (OPTIONAL):

The salivary cortisol assay will be processed at the lab at CSMC which is then shipped to Quest Diagnostics. It is stable at room temperature for 5 days. The assay is performed using liquid chromatography/tandem mass spectrometry. While cortisol has a diurnal variability with levels highest in the early morning, we will be assessing percent change of cortisol levels over the 10 minutes of the VR demonstration or Health and Wellness channel viewing in each individual. This will minimize the effect of the diurnal variation.

Data Collection

We will collect the following information about VR intervention and Control participants:

- Name and Medical Record Number (secured and stored separate from all other data below)
- Age
- Sex
- Race/Ethnicity
- Admitting Diagnosis during inpatient stay
- ISP ward
- Previous diagnoses of epilepsy and other neurological or visual impairments.
- All Pain ratings throughout the hospital stay.
- All opioid and non-opioid pain medication usage information (dosage amount and timing).
- HCAHPS Patient Satisfaction Picker Survey responses.

Demographic and descriptive clinical data will be abstracted by [name] or authorized study staff at the time of patient selection, and vital signs will be collected before and after the intervention.

Analysis Plan:

The current study plan allows us to enroll an average of three patients per week at a minimum.

We will calculate descriptive statistics for patients in each group. We will then perform bivariate analyses to compare mean cumulative pain scores, morphine milligram equivalents, and average length of stay between groups using t-tests. We will compare the proportion with an opioid complication between groups using chi-squared, and calculate the “number needed to treat” in order to prevent one additional complication with VR vs. no usual care. We will then perform multivariable linear regression analysis to predict pain scores while controlling covariates, including age, demographics, comorbidities, and baseline pain scores. We will report both intention-to-treat analyses including all evaluable patients

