by randomized allocation, and per-protocol analyses limited to just those patients in the intervention arm who opt to use VR (while accounting for dose-response potential). We will adopt a P-value of <0.05 as evidence for statistical significance, and calculate 95% confidence intervals around point estimates. All analyses will be performed using Stata for Windows (StataCorp, College Station, TX).

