We have powered this study based on our previous research on pain management with VR¹⁸⁻²⁰, which reported clinically meaningful shifts of approximately 1 SD in self-reported pain scores following brief exposure to VR. Several previous studies²¹⁻²³ have established that the minimal clinically important difference on patient-reported pain rating scales (visual analog or numerical ratings) is approximately 13% (approximately 1.4 points on a 0-10 scale, with a standard deviation of 14%). Thus, we are interested in measuring a 1SD change in pain ratings following exposure to the VR intervention, but we will collect a sufficiently large sample to measure smaller changes both within patients exposed to VR, and in comparison to a control group. For all analyses, we will assume a 5% Type I error rate (alpha) and a 20% type II error rate (or 80% power). For **within group analyses**, we would require a minimum of 10 patients to detect a 1 SD change in pain scores. However, we have powered the study to detect a 0.38 SD difference **within each group** (with 58 patients per group), however have modified this to 80 patients per group. We used this method to calculate and justify the required sample size for a complete cohort of orthopedic patients. Therefore, the overall intervention and control groups, along with the orthopedic subgroup will be adequately powered for analysis. The sample-size modification is required due to over-estimation of adherence, and aims to support a "per-protocol" analyses. We plan on conducting this per protocol analysis among treatment-compliant subjects *in addition* to the intent to treat analysis. The additional subjects, then, will bring the total N of the per-protocol analysis into a range capable of detecting the hypothesized effect-size used in the original sample-size calculation. While sample-size re-estimation based on observed difference with a limited number of subjects may be biased and misleading, we feel that the goal of the trial (determining efficacy rather than effectiveness) - coupled with the fact that randomization procedures will remain unchanged - supports the request.

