For **between group analyses**, we will compare pain scores obtained from all inpatients exposed to the VR intervention to a **80-patient control group**. We expect the variability in pain scores to be comparable to that observed in VR intervention participants (approximately 1 SD change over a 20-minute period, equivalent to an effect size of 1.0), so we are collecting data from the same number of patients (80) with complete data in Phase 2. We have powered this study to detect an SD difference as low as 0.52 between the VR intervention and control participants (requiring 80 patients in each group).

We will conduct an exploratory **subgroup analysis** to detect changes in salivary cortisol between patients exposed to VR vs patients exposed to the control intervention.

As of September 2017, 9 patients have been consented to participate in this sub-study, but only 1 patient yielded sufficient quantity of samples for a pre- and post-intervention cortisol analysis. The majority of samples were of inadequate quantity for laboratory analysis. Given that all participants eligible to participate in the main study are also eligible for this sub-study, each patient consenting to the main study will be asked to participate in the cortisol sub-study. Accounting for attrition and the

technical complexities of cortisol sampling that often results in low yield quantities, we will recruit 113 patients total (including the 9 that have already been consented as of September 2017).

Risks and Benefits:

Benefits:

To Individual: Patients will likely enjoy using the VR interventions, which are immersive and impressive upon cursory use. We anticipate that patients may report greater satisfaction, pain management, and overall health during the study.

To Society: This will be one of the first RCTs conducted on inpatient use of VR for pain management. Knowledge gained could be used to improve patient satisfaction with care and pain management across all hospitals.

Risks:

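### The 0.52 SD behind the between-group power is motivated only by short-term change after VR, is not justified for the stay-long cumulative pain score that is tested, and does not pair with 80 per group at 80% power

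*Combined protocol and SAP*

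**What the plan says.** **Power basis.** The sample-size text under Analysis Plan cites earlier work by the same group, in which pain scores shifted by about 1 SD after brief VR exposure. The between-group paragraph repeats this as "approximately 1 SD change over a 20-minute period, equivalent to an effect size of 1.0", in a sentence about how variable control patients' scores are expected to be. For all analyses, "we will assume a 5% Type I error rate (alpha) and a 20% type II error rate (or 80% power". The between-group target is: "We have powered this study to detect an SD difference as low as 0.52 between the VR intervention and control participants", with the parenthesis "requiring 80 patients in each group". The within-group target is 0.38 SD with 58 per group, later raised to 80 because adherence had been over-estimated. No adherence rate is given.

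**Outcome tested.** The Analysis Plan will "compare mean cumulative pain scores, morphine milligram equivalents, and average length of stay between groups using t-tests", followed by linear regression for pain adjusted for baseline pain and other covariates. Data Collection takes all pain ratings from the whole stay. Under Pain Ratings, "patients will not be asked about pain as part of the study"; the scores are those recorded in routine care. VR is used as needed for up to 20 days.

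**A second comparison, named only.** Overview and Study Design says that pre/post changes in pain will be assessed between the arms. The Analysis Plan gives this no rating rule, time window or test.

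**The concern.** The effect that motivates the design is a change around a single exposure. The quantity in the t-test is pain accumulated over days, from ratings taken whenever nursing staff recorded them, many presumably when VR was not in use. An effect in SD units does not carry over automatically: the mean difference may be diluted and the SD of the summary will differ from that of a single rating. If cumulative means a sum, the score also grows with length of stay, which is itself an outcome.

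If this is left as it is, a null result on stay-long pain could be reported as coming from a trial powered for 0.52 SD, although nothing shows that 0.52 SD is plausible for that score. A real session-level effect could go unreported because the comparison that would show it has no specification.

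**Working it through.** **Inputs.** Alpha 5%, taken as two-sided because the plan does not say; 80% power; 0.52 SD between groups; 0.38 SD and 1 SD within group; 58 and 80 per group; 122 per group overall. All are from Analysis Plan, except 122, from Study Population and Period. Normal approximations are shown; the t-based value follows and is the one used.

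**1. The plan's own figures.**
- Within group, 1 SD: paired t-test gives n = 9.9, so 10. This matches the plan.
- Within group, 0.38 SD: (1.960 + 0.842)² / 0.38² = 7.849 / 0.1444 = 54.4; paired t gives 56.3, so 57. The stated 58 is consistent.
- Between groups, 0.52 SD: n = 2 × 7.849 / 0.52² = 15.698 / 0.2704 = 58.1; t gives 59.03, so 60 per group. The stated 80 does not reproduce. A one-sided test would need fewer still (46 by normal approximation).

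**2. What 80 per group delivers.**
- Power at 0.52 SD: 0.52 × √(80/2) = 3.289; Φ(3.289 − 1.960) = 0.908; t gives 90.5%.
- Detectable difference at 80% power: 2.802 × √(2/80) = 0.443; t gives 0.446 SD.
- With 58 per group: 0.52 × √29 = 2.800; Φ(0.840) = 0.800; t gives 79.3%.

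So 0.52 SD belongs with the earlier 58 per group. Going from 58 to 80 equals an allowance of 1 − 58/80 = 27.5%, which the plan does not state.

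**3. Did 1 SD set the sample size?** No. A 1 SD between-group difference needs 16.7, so 17 per group.

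**4. Power for the cumulative score.** It cannot be computed, because the plan gives neither an SD nor an expected difference for it. By assumed true standardized difference, power at 80 per group is 24% at 0.20, 47% at 0.30, 71% at 0.40 and 90.5% at 0.52.

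**5. Dilution, for illustration only.** Assume a 1 SD benefit on a share s of a patient's ratings and none on the rest, with the outcome taken as a per-patient average. The standardized difference is s / f, where f is the SD of the average relative to that of one rating. Two cases: f = 1 (no gain from averaging), and f = √[(1 + 11 × 0.5)/12] = 0.736 (12 ratings, within-patient correlation 0.5). The shares, number of ratings and correlation are assumptions; none is in the plan.

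| Share s | s / f, f = 1 | Power, 80 per arm | s / f, f = 0.736 | Power, 80 per arm |
|---|---|---|---|---|
| 1/12 | 0.083 | 8% | 0.113 | 11% |
| 1/6 | 0.167 | 18% | 0.226 | 30% |
| 1/3 | 0.333 | 55% | 0.453 | 81% |

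The share needed for 80% power at 80 per arm is 0.446 × f: about 45% when f = 1 and about 33% when f = 0.736.

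**The case against.** The strongest reply is that a calculation in SD units is valid for a t-test on any continuous outcome, provided the true difference is 0.52 of that outcome's SD. That stands. A reader might infer that the stated power is wrong for the cumulative score, or that the trial is underpowered; the documents show neither. What is missing is a reason to expect 0.52 SD on that score.

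A reader might also infer that the trial was sized on 1 SD. It was not: 0.52 SD and 0.38 SD set the numbers, and the plan says it wants to measure changes smaller than 1 SD. The 1 SD is the motivation and, awkwardly, a statement about variability.

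The stay-long outcome is deliberate: the design overview speaks of long-term pain management, and the aims concern the hospital stay. That stands too, so it should be kept. A pre/post comparison is also already intended, and patients in both arms log the start and duration of viewing, so ratings can be linked to sessions afterwards. The gap is in specification.

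On the 80, the plan attributes the increase to adherence and wants a per-protocol analysis that can detect the original effect. That may well explain the number, but no rate is given and the text presents 80 as the requirement for 0.52 SD.

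Finally, nothing should be made of 20 minutes against a 10-minute first session. The 20 minutes is the period over which pain changed, and first use may run to 30 minutes.

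**Conclusion.** The point holds in two limited parts.

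First, the stated power is unsupported for the t-test on cumulative pain: the motivation is short-term change, the score is undefined, and it has no SD or expected difference. The size of any shortfall is unknown. The dilution figures show only that the answer depends on quantities the plan does not give. At a one-third share, power moves from 55% to 81% on the SD assumption alone; at one-sixth or less it is 30% or lower in both cases.

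Second, the pairing of 0.52 SD with 80 per group at 80% power is arithmetically wrong, assuming a two-sided 5% test. About 60 per group suffices for 0.52 SD, and 80 per group detects 0.446 SD. This error is in the conservative direction, so it does not threaten the trial, but it leaves the reader unsure which difference the design targets.

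**What to change.** 1. Specify the pre/post comparison named in Overview and Study Design: the last charted NRS before the first session and the first charted NRS within a fixed window after it, with the same window in the TV arm, compared between arms with adjustment for baseline.
2. Keep stay-long pain alongside it, defined as a per-patient average so that it does not grow with length of stay.
3. For each outcome, restate the detectable difference using the SD in patients enrolled before October 2017, pooled over arms so that no treatment difference enters. Those patients had mixed diagnoses, so say whether the same SD is expected in the orthopedic cohort.
4. Correct the pairing: either 0.52 SD with about 60 per group, or 80 per group with 0.446 SD. If 80 includes an adherence allowance, state the rate.
5. Delete the effect size of 1.0 as a variability assumption.

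The cost is SAP wording and one query of chart data already being collected. The main drawback is that some patients will have no rating inside the window; the plan should say how they are handled and report their number by arm.

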- **Iceland Flyover:** Patients fly over photorealistic views of world landmarks, allowing them to visit famous places from the hospital bed.

3a. Iceland Flyover

- **Pain RelieVR:** Patients are immersed in a fantasy world where they use their gaze to direct objects at moving targets, while exposed to colorful imagery and soothing music.

3b. Pain RelieVR

- **Anxiety RelieVR:** Patients experience an interactive, meditative landscape along a peaceful shoreline.

3c. Anxiety RelieVR

Study Population and Period

The overall study population will consist of up to 244 patients – 122 patients who are exposed to VR, and 122 control patients exposed to an audiovisual “sham” intervention. We will randomize patients using the MS Excel random number generator. We will select up to 244 hospitalized patients at CSMC admitted during the study period of 1 October 2016 to 30 September 2018. The inpatient wards serve patients ranging in age from 18 to over 100, allowing us to assess the feasibility of using VR across diverse age groups. Initially, we did not restrict eligibility to any particular diagnosis, although we will collect this demographic information for subsequent subgroup analysis. All participants were selected at random by the Co-Investigator ([name]), by investigators in the gastroenterology service (Drs. [name] and [name]), or the Heart Institute (Drs. [name], [name], and [name]) or psychiatry service (Drs. [name] and [name]), or any CSMC physician who wishes to refer patients who meet the eligibility

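### The plan says that detecting 0.52 SD between groups requires 80 patients per group; at its own alpha and power it requires about 60, and the adherence allowance that might explain 80 is not stated

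*Combined protocol and SAP*

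**What the plan says.** All the statements are in the combined protocol and SAP, mostly under Analysis Plan.

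- **Error rates.** For all analyses, "we will assume a 5% Type I error rate (alpha) and a 20% type II error rate (or 80% power". Sidedness is not stated. The plan uses P<0.05 with 95% confidence intervals and compares mean pain scores by t-test.
- **Within-group sample size.** The study was powered for 0.38 SD within each group, "with 58 patients per group), however have modified this to 80 patients per group".
- **Reason for the change.** "The sample-size modification is required due to over-estimation of adherence". The added patients are meant to "bring the total N of the per-protocol analysis into a range capable of detecting the hypothesized effect-size used in the original sample-size calculation". No adherence rate is given.
- **Between-group sample size.** The study is powered to "detect an SD difference as low as 0.52 between the VR intervention and control participants (requiring 80 patients in each group". The same paragraph refers to "the same number of patients (80) with complete data in Phase 2".
- **Analysis sets.** The plan has "intention-to-treat analyses including all evaluable patients" by allocation. It also has a per-protocol analysis that, on the intervention side, keeps only patients who choose to use VR.

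**The concern.** This is the plan's only sample-size statement for the comparison of VR with control, which is the trial's main question. It gives three quantities: effect size, number per group, and (from the preceding paragraph) alpha and power. Any two should determine the third, and here they do not.

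The stakes are modest but real. The 80 per group underlies the 160-patient orthopedic cohort. A reader needs to know whether 80 is the number analysed, which gives more sensitivity than claimed, or a number enlarged so that enough adherent patients remain for the per-protocol analysis. In the second case the size of the enlargement depends on an adherence rate that the reader cannot see or compare with observed use.

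**Working it through.** **Inputs.** Alpha 0.05 and power 0.80 (Analysis Plan); two-sided (assumed); effect 0.52 in SD units, so SD = 1; equal groups; two-sample t-test. Normal quantiles are 1.960 and 0.8416.

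**1. The plan's within-group figures reproduce.** By the paired t-test, 1 SD needs 9.94, so 10 patients, as stated. For 0.38 SD, 56.3 are needed, so 57, and 58 patients detect 0.374 SD. The plan's method is therefore the standard one.

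**2. The stated 80 does not reproduce.**

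- Normal formula: n = 2 × (1.960 + 0.8416)² / 0.52² = 58.05, so 59 per group.
- Noncentral t: n = 59.03, so 60 per group (power 0.7998 at 59 and 0.8065 at 60).

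**3. Other settings that might give 80.**

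| Setting for 0.52 SD | Per group (normal / t) |
|---|---|
| Two-sided 5%, 80% power (the plan) | 59 / 60 |
| One-sided 5%, 80% power | 46 / 47 |
| Two-sided 5%, 85% power | 67 / 68 |
| Two-sided 5%, 90% power | 78 / 79 |

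A one-sided test moves further from 80. Power of 90% comes close but contradicts the stated 80%. A 25% loss from both arms also gives 80 (60 / 0.75 = 80), but the plan states no such rate.

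**4. What 58 and 80 per group deliver.** The detectable difference at 80% power by the normal formula is (1.960 + 0.8416) × √(2/n).

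| Per group | Detectable SD (normal / t) | Power for 0.52 SD (normal / t) |
|---|---|---|
| 58 | 0.520 / 0.525 | 80.0% / 79.3% |
| 80 | 0.443 / 0.446 | 90.8% / 90.5% |

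So 0.52 SD goes with 58 per group, and 80 per group goes with about 0.45 SD.

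**5. If 80 is an adherence allowance.** The non-adherence it can absorb while keeping 80% power for 0.52 SD (t-test) depends on which arms are filtered.

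- Both arms fall to 60: 1 − 60/80 = 25%.
- Only the VR arm is filtered and all 80 controls stay: 47 VR patients against 80 controls give power 0.802 (46 give 0.796), and 1 − 47/80 = 41%.

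These are tolerances, not estimates of the rate the sponsor assumed.

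**The case against.** The strongest reply is that the plan explains the number. It says adherence had been over-estimated, and that the extra patients are there to keep the original effect size within reach of the per-protocol analysis. On that text, holding 0.52 SD fixed while raising 58 to 80 is deliberate. The requirement then means 80 recruited so that enough adherent patients remain. The error, if there is one, is also on the safe side, and no enrolment target or test depends on it.

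Much of this stands. A reader might infer that 0.52 SD is simply a leftover that nobody revised when the size changed. The match with 58 fits that, but it fits the stated intention equally well, so the documents do not settle it. A reader might also infer that describing the 80 as having complete data rules out an adherence allowance. It does not: under Pain Ratings and Post-Intervention Procedures, pain scores come from the health record, so a patient who never uses VR can still have complete data.

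What the reply does not repair is the sentence itself. It states a requirement for 0.52 SD, with no mention of inflation or of the per-protocol set, under an 80% power rule that covers all analyses. Without a rate, the step from 58 to 80 cannot be checked.

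**Conclusion.** The statement is wrong as written. At two-sided 5% alpha and 80% power, 0.52 SD between groups requires 59 to 60 patients per group, not 80. If 80 per group are analysed, the plan understates its own sensitivity: power is about 90% for 0.52 SD, or 80% for about 0.45 SD. A reader might infer an underpowered trial; these figures point the other way for the intention-to-treat comparison.

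The adherence explanation may account for 80, but it is incomplete because the rate and the arms it applies to are missing. It would also be tempting to read a single implied non-adherence rate of 25% (or 27.5%, from 1 − 58/80) off the numbers. That assumes equal loss in both arms. The plan's definition of the per-protocol set restricts the VR arm, and on that reading about 41% could be tolerated.

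The result rests on a two-sided test, equal groups of 80 and equal SDs. A one-sided test would widen the gap. The point deserves correction, but it does not threaten the design.

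**What to change.** In the between-group paragraph of the Analysis Plan:

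1. State that 0.52 SD at 80% power and two-sided 5% alpha needs about 60 analysed patients per group.
2. State that 80 per group analysed by intention to treat detects about 0.45 SD at 80% power, or 0.52 SD at about 90% power.
3. If 0.52 SD is kept as the per-protocol target, label it so, and give the adherence rate assumed and the arms it applies to. For reference, 80 per group tolerates about 25% non-adherence if both arms fall to 60, and about 41% if only the VR arm is restricted (47 against 80).

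The cost is wording only. Enrolment and analyses do not change. The third item also needs the sponsor to supply the adherence rate behind the increase.
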